15.3 INTENT-TO-TREAT AND EVALUABLE SUBJECT POPULATIONS

The intent-to-treat population is defined as the subjects who are randomized and receive the first day's study agents. The evaluable population is defined as the subjects who are randomized, meet

all of the inclusion and exclusion criteria, and who contribute at least four (4) usable on-study urine samples and 21 days of self report of methamphetamine use/non-use by SUR.

15.4 ANALYSIS PLAN

15.4.1 Efficacy Assessments

Each primary and secondary efficacy outcome measure will be analyzed for the intent-to-treat and for the evaluable population. Major differences in the results, if any, will be further explored. While there is every intent to be complete in describing the analyses to be performed, it is not possible to anticipate every contingency and some adjustments may be required to meet constraints posed by the structure of the data.

All statistical tests will be two-sided at a 5% Type I error rate. Confidence intervals will be two-sided with a 95% confidence coefficient.

Primary Efficacy Outcomes

The weekly mean proportion of methamphetamine-free urines on study will be compared between treatment groups using Generalized Estimating Equations (GEE) for ordinal categorical response (Lipsitz *et al.*, 1994). GEE provide a model-based regression method applicable for the analysis of the correlated data that will result from this repeated measures longitudinal study. The GEE procedure was first proposed by Liang and Zeger (1986) and Zeger and Liang (1986) and models the population average. GEE has several useful features:

- 1. It can be used to analyze different types of outcomes such as continuous, binary, or count.
- 2. It can be used to analyze an unbalanced design caused by either differing numbers of observations per person or by observations taken at different times.
- 3. The parameter estimates are consistent even if assumptions about the variance structure are not completely accurate.

Secondary Efficacy Outcomes

Unless the primary response analysis implies the need for a more elaborate model, between group comparisons of the secondary outcomes will be performed as follows:

Outcome Measure	Test
A, C, G, I, J	Chi-square tests
D, E, G, L, Q	Analysis of Variance
B, F, H, K, L, M, N, O, P	GEE
R	Wilcoxon (Gehan)

S. Adverse events, laboratory data, physical exams, and vital signs will be reported in tabular form. AEs will be listed indicating the frequency of each type of event. The frequencies of adverse events by type will be compared between study arms using Chi-square analyses.

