15.1.2 Secondary Outcomes Measures

Effect on methamphetamine and other drug use during the 8 week treatment period

- B. Proportion of subjects with 3 consecutive weeks of abstinence as measured by 9 consecutive methamphetamine-free (<300 ng/ml) urine samples.
- C. Weekly mean proportion of methamphetamine non-use days based on subject's self report of use (SUR) during the 8-week treatment period.

- D. The proportion of subjects who decrease the overall proportion of methamphetamine use to 50% or less of their use in the month prior to the study based on timeline followback for the before study period and self report using the SUR during the on study period.
- E. The maximum number of consecutive methamphetamine non-use days by subject's self report of use (by SUR).
- F. The number of methamphetamine-free urines during the 8-week period.
- G. Weekly mean proportion of non-use days of other drug use, by other drug according to SUR including marijuana, nicotine, and alcohol.
- H. Number of negative urines for tetrahydrocannabinol, cocaine, amphetamines, barbiturates, opiates, and benzodiazepines, and negative alcohol breathalyzer tests.
- H. Log weekly median quantitative urine methamphetamine levels.
- I. Proportion of subjects who reduce overall median of methamphetamine quantitative urine concentration to 50% of his/her baseline values.
- J. Proportion of subjects who reduce the overall median of methamphetamine quantitative urine concentration to 25% of his/her baseline value.

Reduction in the severity of methamphetamine dependence, craving, and withdrawal

- K. CGI-O scores (dependence).
- L. CGI-S scores (dependence).
- M. ASI-Lite composite score of the drug section and methamphetamine use question individually (dependence) and composite scores of the other sections (other global measures of improvement).
- N. BSCS scores (craving)
- O. MAWQ scores (withdrawal)

Severity of Depression

P. HAM-D scores.

Changes in Cognitive Functions

Q. Change in cognitive function at study end compared to baseline.

Treatment Retention

R. Number of days in treatment.

Safety of Ondansetron

S. AEs, laboratory data, physical exams, ECG results, and vital signs.

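### Secondary outcomes B to the first H are one letter out of step with the test table, leaving the weekly self-report outcomes (C, G) without a repeated-measures test and G and L with two tests each

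*Protocol*

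**What the plan says.** Section 15.1.2 of the protocol lists the secondary outcomes by letter. The list runs from B to S, has no A and uses H for two different outcomes. The entries that matter here are:

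- B: "Proportion of subjects with 3 consecutive weeks of abstinence as measured by 9 consecutive methamphetamine-free" urines, one yes/no result per subject.
- C: "Weekly mean proportion of methamphetamine non-use days based on subject's self report of use (SUR) during the 8-week treatment period", up to eight values per subject.
- D: "The proportion of subjects who decrease the overall proportion of methamphetamine use to 50% or less of their use" in the month before the study, one yes/no result per subject.
- G: "Weekly mean proportion of non-use days of other drug use, by other drug", again up to eight values per subject for each substance.
- L: CGI-S, which section 13.6.24 schedules weekly during treatment.

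Section 15.4.1 states that "between group comparisons of the secondary outcomes will be performed as follows" and gives a table by letter:

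- chi-square: A, C, G, I, J
- ANOVA: D, E, G, L, Q
- GEE: B, F, H, K, L, M, N, O, P
- Wilcoxon (Gehan): R

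The same section justifies GEE for the primary outcome by the correlation among repeated measures on a subject. Section 16.3 says the analysis will follow the analytical plan section of the protocol, so this table is an operative rule.

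**The concern.** Read literally, the table gives the weekly self-report outcome C a test for independent counts, and gives G that test plus an ANOVA that takes no account of repeated weeks. An analyst following the protocol would have to pool correlated weeks or days, dichotomise each subject, or depart from the table. Which of these happens is not fixed. G and L each carry two tests, so two p-values compete for one outcome, and the chi-square row begins with an outcome that does not exist.

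The self-report outcomes are not incidental. Section 5.2 names weekly non-use days among the secondary objectives, section 15.2.2 states a hypothesis on them, and section 8.2 suggests that self-report may be more sensitive than urine testing to small effects. At stake is a pre-specified, valid test for these outcomes.

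**Working it through.** The plan gives no figure to reproduce here. The check sets the two sections side by side and then sizes the worst case.

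**Step 1. Letter by letter.** The last column reads the table with B to the first H moved back one letter.

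| Listed as | Outcome (paraphrased) | Data per subject | Test as printed | Test after moving back one letter |
|---|---|---|---|---|
| B | nine negative urines in a row | one yes/no | GEE | A: chi-square |
| C | weekly methamphetamine non-use days | up to 8 values | chi-square | B: GEE |
| D | use at least halved | one yes/no | ANOVA | C: chi-square |
| E | longest run of non-use days | one number | ANOVA | D: ANOVA |
| F | count of methamphetamine-free urines | one count | GEE | E: ANOVA |
| G | weekly non-use days, other drugs | up to 8 values | chi-square and ANOVA | F: GEE |
| first H | negative other-drug urines and breath tests | counts | GEE | G: chi-square and ANOVA |
| second H | log weekly median urine level | up to 8 values | GEE | unchanged: GEE |

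From the second H to R the letters agree. The offset therefore covers 7 of 18 lettered outcomes (S, safety, is handled separately) and ends at the duplicated H. After the move, both yes/no outcomes get chi-square, both weekly proportions get GEE, and the per-subject run and urine count get ANOVA. That pattern points to a lettering slip. Two double entries remain: table letter G (now the first H) and table letter L (CGI-S).

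**Step 2. Do B and D matter in practice?** GEE with one observation per subject reduces to ordinary regression with robust standard errors, so B is redundant and not invalid. For D, the Pearson chi-square on a 0/1 outcome equals N × R², and R² = 3F / (3F + N − 4) for four arms. With 45 per arm (section 15.5), N = 180, and the 5% F cut-off on 3 and 176 df is 2.656. Then 3F = 7.968, R² = 7.968 / 183.968 = 0.0433, and N × R² = 7.80, against the chi-square cut-off of 7.81. The two tests give practically the same answer.

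**Step 3. Worst case for C and G if weeks are pooled.** The protocol gives no week-to-week correlation (ICC), so it is assumed over a range. With m = 8 weeks the design effect is 1 + (m − 1) × ICC. A four-arm test that treats 180 × 8 = 1,440 values as independent rejects when 3F exceeds 7.83, whereas the statistic is actually inflated by the design effect. The error rate is therefore about P(χ² on 3 df > 7.83 / design effect).

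| Assumed ICC | Design effect | 7.83 / design effect | Type I error |
|---|---|---|---|
| 0.1 | 1.7 | 4.61 | about 20% |
| 0.3 | 3.1 | 2.53 | about 47% |
| 0.5 | 4.5 | 1.74 | about 63% |
| 0.7 | 5.9 | 1.33 | about 72% |

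Simulation with no treatment effect agrees: 47–48% at ICC 0.3 and 63% to 64% at 0.5, for 30 or 45 per arm. Pooling 7 × 8 = 56 days is worse: at a day-level ICC of 0.05 the design effect is 1 + 55 × 0.05 = 3.75, giving about 55%. With one summary value per subject, simulated error stayed between 4.5% and 6%.

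**The case against.** The strongest reply is that the inflation does not follow from the text. Neither section says that weeks or days are the unit of analysis. A weekly mean over the treatment period can be reduced to one value per subject, and ANOVA on that value is valid. If the mismatch is a lettering slip, a pooled analysis was never intended. This stands. A reader might infer that the plan commits the trial to a 47% false-positive rate, but the documents do not support that. They support only that C and G lack a suitable named test.

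A reader might also infer that the whole table is misaligned, or that B and D have invalid tests. Neither holds: 11 of the 18 outcomes line up, B under GEE is redundant, and D under ANOVA is almost identical to chi-square. Nor do the documents say that a false positive on self-report would by itself trigger later studies. Section 5.1 speaks of the results in general, section 15.4.3 bases the dose-response curves on the primary outcome, and section 15.5 calls this a pilot.

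Other defences are weaker. The allowance in 15.4.1 for adjustments or a more elaborate model corrects no letter and defers the choice until data are seen. A missing A might be a lost list entry, but restoring one in front of B would leave C, G and L with the same tests. A separate analysis plan could repair the table, but the point is a wrong stated rule and not a missing detail.

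**Conclusion.** The mismatch is real and is visible without any assumption. Outcomes B to the first H are one letter out of step with the test table. The consequential cases are C (chi-square only), G (two tests, neither named as a repeated-measures method), L (two tests) and the test for a non-existent A. F and the first H, per-subject counts sent to GEE, are mismatched in the same harmless way as B.

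The statistical size is conditional. Error well above 5%, for example about 47% at an assumed ICC of 0.3, arises only if weekly values are pooled as independent; a single summary per subject holds about 5%. These are secondary outcomes in a pilot trial, so the table should be corrected, but the primary analysis is untouched.

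**What to change.** Restate the table in 15.4.1 by outcome name, with one test each, and give the list in 15.1.2 unique letters:

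- weekly non-use days for methamphetamine, and for other drugs: GEE with subject as the cluster
- nine-consecutive-negative success and 50% reduction in use: chi-square
- longest run of non-use days and number of methamphetamine-free urines: ANOVA
- number of negative other-drug urines and breath tests (first H): a single per-subject test, ANOVA, with the chi-square entry removed; re-lettering alone would leave this outcome with two tests
- log weekly median urine level: GEE
- CGI-S: GEE only, with L removed from the ANOVA row
- all remaining letters: unchanged

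The cost is one corrected table, in the protocol or carried into the analysis plan, before unblinding. It needs no new data, subjects or procedures.

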4.6 SAFETY OF ONDANSETRON

Ondansetron's Approved Use. Ondansetron is currently approved as an antiemetic agent and is safe and effective for the prevention of nausea and vomiting in postoperative patients and in patients treated with chemotherapy or radiotherapy (Needles et al., 1999; Tramer et al., 1997a; Tramer et al., 1997b; Tramer et al., 1998; Tramer et al., 1999). Both intravenous and oral doses of 4-16 mg are common in repeated and subacute (4-14 days) dosing regimens. Overall, few side effects are reported. A review of 14,800 patients treated with ondansetron found headache and diarrhea to be most common adverse events (Bryson, 1992). In chemotherapy patients receiving cisplatin, the incidence of headache was dose related and ranged from 17 to 26% following intravenous ondansetron doses ranging from 1 to 20 mg. The degree of headache or diarrhea is rarely severe and there is no reason to expect that chronic methamphetamine use will exacerbate these side effect profiles.

Rare Adverse Reactions. No systematic empirical evidence has associated ondansetron with the development of extrapyramidal symptoms. Nevertheless, there are case reports in a total of six patients describing such symptoms (Dobrow et al., 1991; Garcia-del-Muro et al., 1993; Halperin and Murphy, 1992; Krstenansky et al., 1994; Mathews and Tancil, 1996). Importantly, unlike antipsychotic medications which do cause extrapyramidal symptoms, ondansetron does not block post-synaptic dopamine receptors. Instead, ondansetron inhibits dopamine release via 5-HT₃ receptors on post-synaptic neurons. Since this dopamine inhibition occurs primarily at suprabasal levels of stimulation, there is little mechanistic reason to expect that ondansetron would cause extrapyramidal symptoms (Costal et al., 1988; Costal et al., 1990c; Costal et al., 1990d; Costal and Naylor 1992; Costal, 1993). All reported cases of extrapyramidal symptoms occurred with intravenous ondansetron administration and none were observed with oral dosing which is the route of administration for the present study. While the risk of extrapyramidal symptoms is extremely small, we will closely monitor patients for this potential side effect.

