5.2 SECONDARY OBJECTIVES

Secondary objectives include:

- 1. Determining the safety of ondansetron in the study population.
- 2. Assessing the effective dose of ondansetron in other measures of success in the reduction of methamphetamine use including the proportion of successful subjects with 9 consecutive methamphetamine-free urine samples, the weekly mean proportion of non-use days assessed by self-report of use, the largest number of consecutive methamphetamine non-use days also assessed by self-report of use, and reductions in use as assessed by self-report compared to baseline (30 day history of use assessed by timeline followback).
- 3. Assessing the efficacy of ondansetron in reducing the severity of methamphetamine dependence [assessed by ASI-Lite (drug composite score principally, but composite scores of each section will also be analyzed, and the methamphetamine use question will be compared separately), and self and observer scored CGI, craving (assessed by BSCS), severity of depression as assessed by HAM-D, and withdrawal symptoms (assessed with a MAWQ)].
- 4. Assessing the efficacy of ondansetron in increasing the number of non-use days of other substances of abuse (marijuana, nicotine, and alcohol) as determined by self-report, and the number of negative urine specimens by individual drug (tetrahydrocannabinol, cocaine, amphetamines, barbiturates, opiates, and benzodiazepines), and the number of negative alcohol breathalyzer tests.
- 5. Assessing the effects of ondansetron on cognitive functions.
- 6. Collecting preliminary information on biological or psychosocial characteristics of patients who may show better responsiveness to ondansetron treatment. In particular, biological and psychological measures reflecting individual differences in serotonergic function.

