8 STUDY DESIGN

8.1 EXPERIMENTAL DESIGN

This is a double-blind, placebo-controlled, randomized, four arm dose-ranging study comparing three dose levels of ondansetron (0.25, 1.0, and 4.0 mg, b.i.d.) to placebo administered to methamphetamine dependent outpatients. Randomization strata include investigational site, age of onset of methamphetamine use (early onset, \leq 17 years of age, versus late onset, > 17 years of age), and frequency of methamphetamine use (current high, > 10 days versus low, \leq 10 days of use in the last 30 days). All subjects will receive a base of standardized, manual-driven CBT (a 90 minute group session three times per week) over 8 weeks of treatment (Huber *et al.*, 1997, Rawson *et al.*, 1995, Shoptaw *et al.* 1994). A final follow-up assessment will be conducted 4 weeks after completion of treatment.

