15.4.3 Dose Response Analysis

Dose response curves will be generated using the slope of the GEE for the primary outcome measure. The frequency and severity of adverse events will be presented for each dose. The shape and the location of the population (group) average dose response will be evaluated for positive outcomes and adverse events to select the best dose for larger phase 2 studies.

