15.5 SAMPLE SIZE

There is no data to determine what type of effect ondansetron will have on the study population because this is a pilot study. Based on other clinical trials of drug abuse treatments, 30 evaluable subjects in study arms will give an indication of treatment effect. It was estimated that 30% of subjects will not meet the evaluable subject criteria, thus to obtain 30 evaluable subjects in each treatment arm, 45 subjects will need to be randomized to each arm for a total of 180 subjects randomized and enrolled on the study.

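### The adverse-event comparison rests on a chi-square without an effect estimate, interval or stated use of dose order, so a non-significant result would say little about excess risk

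*Protocol*

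**What the plan says.** The first secondary objective in Protocol 5.2 is "Determining the safety of ondansetron in the study population". The design (8.1) is a "four arm dose-ranging study comparing three dose levels of ondansetron (0.25, 1.0, and 4.0 mg, b.i.d.) to placebo".

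For outcome S, section 15.4.1 has adverse events, laboratory data, physical examinations and vital signs tabulated. It then gives one inferential step: "adverse events by type will be compared between study arms using Chi-square analyses". The general rule in the same section applies: "All statistical tests will be two-sided at a 5% Type I error rate". That section also sets 95% two-sided confidence intervals as the convention, without saying that any will be computed for adverse events.

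Section 15.4.3 states: "The frequency and severity of adverse events will be presented for each dose". Its next sentence has the shape and location of the group average dose response evaluated for both benefit and adverse events, in order to pick a dose for later studies. The synopsis likewise plans dose-response curves to find an effective dose with few side effects.

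The only event rate in the document that bears on dose is in 4.6, for cisplatin patients given 1 to 20 mg intravenously: "the incidence of headache was dose related and ranged from 17 to 26" per cent. No adverse-event rate, effect size or power is stated for this trial.

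**The concern.** The trial is a dose-ranging pilot in which adverse events serve a stated objective and also inform the choice of dose. The background section itself describes the best-known side effect as rising with dose. A chi-square across four arms, in its usual form, gives the same p-value however the arms are relabelled, so it makes no use of the ordering from placebo to 4.0 mg. Nor does it show how large an excess the data leave open.

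With about 45 subjects per arm, a table of non-significant p-values could arise easily even if a common event rose materially with dose. Section 15.4.3 would put event frequencies by dose next to those p-values, but without an interval or an ordered test to say how firmly any gradient is established.

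**Working it through.** **Inputs.** Four arms (8.1) and two-sided 5% (15.4.1). For arm size, 15.5 says "45 subjects will need to be randomized to each arm for a total of 180 subjects randomized and enrolled on the study". The protocol's own figure checks approximately: 30 evaluable ÷ 0.70 = 42.9, so 43 per arm, and 45 × 0.70 = 31.5; 45 is a mild rounding up. The check uses 45 per arm, since adverse events would be assessed in everyone treated. Event rates and dose-response shapes are assumptions, because the protocol gives none for this population.

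**Power of the 3-df chi-square.** Noncentrality λ = n Σ(pᵢ − p̄)² / [p̄(1 − p̄)], with critical value 7.815.

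- 17, 20, 23, 26%: p̄ = 0.215, Σ(pᵢ − p̄)² = 0.0045, λ = 45 × 0.0045 / 0.1688 = 1.20, power 13% (12 to 13% in simulation).
- 17, 22.7, 28.3, 34%: p̄ = 0.255, Σ(pᵢ − p̄)² = 0.01606, λ = 45 × 0.01606 / 0.1900 = 3.80, power 34%.

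**Comparison with a Cochran-Armitage trend test** (simulated, asymptotic, scores 0 to 3, equal steps, 45 per arm):

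| Rates, placebo to top dose | Chi-square | Trend |
|---|---|---|
| 17 to 26% | 12–13% | 19% |
| 17 to 34% | 34% | 50% |
| 17% in all arms (null) | 5% | 5% |

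The trend test's gain is therefore not bought with a higher false-positive rate.

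**Dependence on the assumed placebo rate.** For a doubling in equal steps, chi-square power is 19% at a placebo rate of 10%, 34% at 17%, 42% at 20%, 57% at 25% and 72% at 30%. Miss rates thus run from 81% to 28%.

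**Dependence on shape:**

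| Rates (placebo, 0.25, 1.0, 4.0 mg) | Chi-square | Trend, rank scores | Trend, mg scores |
|---|---|---|---|
| 17, 22.7, 28.3, 34% | 34% | 50% | 42% |
| 17, 17, 17, 34% | 49% | 47% | 64% |
| 17, 34, 34, 34% | 42% | 38% | 18% |
| 10, 10, 30, 10% | 74% | 10% | 3% |

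The choice of scores matters, and a trend test is no general replacement for the chi-square.

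**What an interval would show.** Suppose 8, 10, 13 and 15 of 45 subjects have an event, from placebo to top dose. Expected events are 11.5 per arm and p̄ = 46/180 = 0.2556, so χ² = (3.5² + 1.5² + 1.5² + 3.5²) / (45 × 0.2556 × 0.7444) = 29 / 8.56 = 3.39 and p = 0.34. The top-dose risk difference is 7/45 = 15.6 points with standard error √(0.1778 × 0.8222/45 + 0.3333 × 0.6667/45) = 0.0905. The 95% interval is −2 to +33 points. The p-value alone conceals that upper limit.

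**Sparse events.** The expected count per arm is 45p, which is below 5 when p is under about 11% (45 × 0.11 = 4.95). The chi-square approximation is doubtful for such event types.

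**The case against.** The strongest reply has four parts.

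1. The protocol says only chi-square analyses. It does not say four-arm, 3-df or unordered; pairwise tests or a chi-square for trend would also fit. The exact form, sparse-cell handling and extra table columns can properly be settled in a statistical analysis plan. This stands in part: unordered is the natural reading and not a stated fact. But 15.4.1 does name the method, and 16.3 says the analysis follows the protocol's analytical plan section.

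2. A reader might infer that the protocol ignores dose order for adverse events, or that a row of non-significant tests will be taken as proof of safety and decide the dose. The documents do not support either. Section 15.4.3 plans an adverse-event dose-response evaluation, and nothing ties dose choice to chi-square significance. What remains is that this evaluation is descriptive.

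3. A reader might take from the 17% to 34% case that the test misses a dose-related doubling two times in three as a general property. That is one assumed rate with one assumed shape. The 17% to 26% in 4.6 is from intravenous dosing in chemotherapy patients, so 17% is not a placebo rate for this trial.

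4. Most of the insensitivity comes from 45 per arm in a self-described pilot. A trend test recovers only part of it and does worse for a plateau or a middle-dose excess. This stands, and it argues for adding to the chi-square and not replacing it.

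**Conclusion.** The point holds as a modest improvement. Section 15.4.1 S gives adverse events a test without an estimate or interval, and 15.4.3 gives them a dose-response look without a method. The power figures of about 12 to 13% and 34% against 19% and 50% apply only if the chi-square is the 3-df test, with 45 per arm, equal-step increases and rank scores for the trend test. Under other assumed placebo rates and shapes they move considerably, as shown. The conclusion that does not hinge on any one setting is that, at this sample size, a non-significant comparison leaves sizeable excess risks open. Even with identical observed counts of 8/45 in two arms, the interval reaches 1.96 × √(2 × 0.1778 × 0.8222/45) = 16 points either way.

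**What to change.** In 15.4.1, outcome S:

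- Keep the chi-square, state that it is the four-arm comparison (if that is meant), and use an exact version when expected counts are small.
- Define the unit as subjects with at least one event of each type, since events are recorded three times a week and repeats in one subject are not independent.
- Add the risk difference of each dose versus placebo with its two-sided 95% confidence interval.
- Add a Cochran-Armitage trend test with prespecified dose scores, and cite it in 15.4.3 as an input to the adverse-event dose response.
- State that a non-significant test is not evidence of no excess.

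The cost is wording and a few table columns; no new data are needed. The trend test is weak for plateau or middle-dose-only patterns, which the retained chi-square and the per-dose intervals cover. The intervals will be wide, and that is the honest message of a pilot this size.
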